7.1 Baseline Considerations

Baseline is defined as the last assessment prior to administration of trial medication.

7.1.1 Disposition

Summary of subject disposition will be presented with the number of randomised, withdrawn, and completed subjects, and frequencies of the analysis sets, in total and by treatment group. Reasons for withdrawal from the trial and premature discontinuations by last visit attended will be presented for the safety analysis set.

Enrolled subjects by country and site will be presented.

7.1.2 Baseline Characteristics and Demographics

Descriptive statistics of demographic and other baseline characteristics will be presented for the safety analysis set.

Demographics will include age, sex, race, ethnic origin, and skin types. Other baseline characteristics will include height, weight, BMI, vital signs, other diagnoses, and concomitant medication (CM). Baseline Actinic Keratosis (AK) characteristics will include anatomical location (face or scalp) and baseline AK count.

Medical history will be summarised by System Organ Class (SOC) and Preferred Term (PT). AK treatment history and history of Squamous Cell Carcinoma (SCC) will be summarised.

For reporting in clinical trial data registries, age group (18-64, 65-84, ≥ 85) will be summarised for all randomised subjects, and age and sex will be summarised for the FAS, safety analysis set, and PP analysis set.

7.2 Exposure and Other Dosing Information

Exposure and other dosing information will be presented for the safety analysis set.

7.2.1 Exposure

The number of treatment cycles received will be presented by country, by anatomical location and by history of SCC.

7.2.2 Compliance

Compliance will be summarised by country and visit, and by visit.

7.2.3 Drug Accountability

The number of used and unused tubes returned will be listed.

7.2.4 Concomitant Medication and Procedures

CM is coded using WHO Drug Dictionary (WHODD) version 2012Q1.

CM at baseline will be summarised by anatomical location and Anatomical Therapeutic Chemical (ATC) level 1 and 4.

Concomitant procedures at baseline will be summarised by anatomical location.

7.3 Analysis of Safety

All safety analyses will be carried out using the safety analysis set unless otherwise stated.

7.3.1 Censoring

Since the primary and secondary safety criteria are time-to-event analyses, a censoring scheme will be defined. This is not detailed in the CCTP.

Subjects from the safety analysis set will be included in the time-to-event analyses, as described in [Table 1](#):

Table 1: Censoring

Event	Date	Outcome
SCC	Date of biopsy	Event
Missing result from a biopsy	Date of biopsy	Censored
Trial completion without SCC	Date of last visit with assessment and no SCC	Censored
Trial discontinuation	Date of last visit with assessment and no SCC	Censored
Death from any cause	Date of death	Censored

SCC: Squamous cell carcinoma

In addition, a PP censoring will be defined, which is censoring at the time when a subject is excluded from the PP analysis set, as described in [Table 2](#):

Table 2: PP censoring

Event	Date	Outcome
Exclusion from PP analysis set with no documented SCC	Date of last visit with assessment before exclusion with no SCC	Censored

PP: Per protocol, SCC: Squamous cell carcinoma

Details on censored subjects are given by subject ID in the analysis set definition document.

Trial ID: LP0041-63	Date: 28-AUG-2019	Version: Final 1.0 Page 10 of 32
---------------------	--------------------------	-------------------------------------

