7.3.2 Primary Safety Criterion

The primary safety criterion is diagnosis of SCC (defined as invasive SCC, i.e. excluding SCC in situ) in the treatment field across the 3-year trial period. Invasive SCC is diagnosed by biopsy.

The CCTP states: “*The 3-year cumulative incidence will be calculated for each treatment group using methods of survival analysis for estimation of cumulative incidence in the presence of censored time-to-event data. Annual incidence rates will also be presented for each group. The cumulative incidence rates will be presented for the event of SCC as primary endpoint and for SCC and other neoplasia as secondary. No formal statistical test comparing the two arms will be performed. For descriptive purposes, as an additional analysis, the difference in cumulative incidence rates between the two arms will be estimated and presented together with its 95% confidence interval.*”

The time to first SCC in months will be calculated as days divided by the average number of days in a month:

$$(\text{Date of biopsy} - \text{date of first exposure to trial medication})/30.4375$$

The cumulative incidence rate with 95% confidence intervals (CIs) will be estimated for each treatment group using SAS *PROC LIFETEST* where the *STRATA* statement will include the randomisation stratification factors *country, anatomical location, and history of SCC*, and with the option *GROUP=treatment*. The incidence rates will be presented using the option *TIMELIST=12 24 36* for 1, 2 and 3 years, respectively. Cumulative incidence will be presented by 1 minus the survival curves estimated using the Kaplan-Meier method. Moreover, numbers at risk and censoring information will be presented by treatment group.

The analysis will be presented for the safety analysis set. In addition, the analysis will be presented for the PP analysis set using PP censoring as described in section 7.3.1. Please see the analysis set definition document for details.

The additional analysis of difference in the 3-year cumulative incidence rates will be calculated as the difference between the Kaplan-Meier estimates of each treatment group and will be presented with 95% CI. The difference is assumed to be approximately normally distributed, and as the treatment groups are assumed to be independent and identically distributed, the 95% CI will be calculated as $\pm 1.96 \times \sqrt{(SE_{Ing}^2 + SE_{Imi}^2)}$ where SE_{Ing} and

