Trial ID: LP0041-63	Date: 28-AUG-2019	Version: Final 1.0 Page 11 of 32
---------------------	--------------------------	-------------------------------------

SE_{imi} are the standard errors (SEs) of the Kaplan-Meier estimates in the ingenol mebutate and imiquimod groups, respectively.

Suspicion of SCC or other neoplasia (Yes/No) will be summarised by visit. The results of biopsies will be summarised by visit and by country.

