7.5 General Principles

7.5.1 Statistical Analysis

In general, all output will be presented by treatment group where nothing else is mentioned. Descriptive statistics for all endpoints will be presented by treatment group and visit (if applicable) using observed cases, i.e. no imputation of missing data will be performed. Summaries by subgroup will include presentation of the endpoint in question by subgroup and overall.

Continuous data will be presented using the number of subjects, mean, standard deviation (SD), median, minimum, and maximum as described in the protocol. In addition, lower and upper quartile will be presented. Both the absolute values and the relative change from baseline will be presented.

Statistical tests will be performed as described in the protocol unless otherwise detailed.

Medical history and AEs are coded using MedDRA version 15.1.

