7.5.3 Handling of Drop-outs and Missing Values

Drop-outs will be handled as described in section 7.3.1 for the primary and secondary safety criteria using censoring in time-to-event analyses.

Missing results from biopsies will be handled using censoring as described in section 7.3.1.

Besides this, no imputation will be implemented.

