Appendix 2.7: Safety Data

Listing 7-1 Deaths

Listing 7-2 Serious adverse events

Listing 7-3 Subjects withdrawn from trial due to adverse events

Listing 7-4 Subjects withdrawn from trial due to LSRs

Listing 7-5 Severe adverse events

Listing 7-6 Adverse events

Listing 7-7 Suspicion of neoplasia and biopsy results

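### Could the rule that censors a subject at an unread biopsy remove a later confirmed SCC from the primary analysis?

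*SAP*

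**What the plan says.** SAP 7.3.1, Table 1, sets the censoring scheme for the safety analysis set. An SCC is an event at its biopsy date. The row "Missing result from a biopsy" is censored at its biopsy date. Completion and discontinuation are censored at the last assessed visit without SCC, and death is censored at its date. SAP 7.5.3 repeats the rule, "Missing results from biopsies will be handled using censoring as described in section 7.3.1", and allows no other imputation. In Table 2, the per-protocol row is conditional: "Exclusion from PP analysis set with no documented SCC".

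SAP 7.3.2 defines the endpoint as a biopsy diagnosis of invasive SCC in the treatment field over the three-year trial and then states: "The time to first SCC in months will be calculated as days divided by the average number of days in a month". The clock runs from first exposure to the biopsy date.

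On reporting, SAP 7.3.2 adds that "numbers at risk and censoring information will be presented by treatment group" and "The results of biopsies will be summarised by visit and by country". SAP 7.5.1 sets the default layout: "In general, all output will be presented by treatment group where nothing else is mentioned". SAP Appendix 2.7 includes "Listing 7-7 Suspicion of neoplasia and biopsy results". SAP 7.3.1 refers to the analysis set definition document for the details of censored subjects; that document is not among those reviewed.

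**The concern.** A subject biopsied on suspicion stays in the trial (protocol 10.1.2) and is assessed through Month 36, so a confirmed SCC after an unread biopsy can be observed. Such a subject fits two rows of Table 1 with different dates and outcomes. The completion, discontinuation and per-protocol rows all carry a no-SCC condition; the missing-result row carries none. If a programmer let the earliest applicable row govern, a confirmed primary-endpoint event and all later follow-up would drop out of the Kaplan-Meier estimate.

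Two features make this look serious. Events are few, so each one counts. Also, biopsies after randomisation are taken because neoplasia is suspected (protocol 10.7.3.1), so censoring at the biopsy is plausibly informative. The only alternative analysis of the primary endpoint is the per-protocol one, which adds censoring and does not vary this rule. The error would lower an arm's SCC rate in a trial designed to measure that risk.

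**Working it through.** **The plan's precision figures.** Protocol 10.3 gives 240 subjects per arm and average upper 95% limits of 2.26% at a 1.0% rate and 4.48% at 2.5%. The Wald limit p + 1.96 × √(p(1−p)/240) gives 2.259% and 4.475%, so both reproduce. Expected SCCs per arm are 240 × 1.0% = 2.4 and 240 × 2.5% = 6.

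**One lost SCC.** Assume 240 subjects followed to Month 36, with one subject having an unread Week 4 biopsy and a confirmed SCC at Month 18.

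| SCCs in the arm | SCC kept | Subject censored at Week 4 | Shift (points) |
|---|---|---|---|
| 6 | 6/240 = 2.50% (SE 1.008) | 5/239 = 2.09% (SE 0.926) | 0.41 |
| 3 | 3/240 = 1.25% (SE 0.717) | 2/239 = 0.84% (SE 0.589) | 0.41 |

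The half-width 1.96 × √(p(1−p)/240) is 1.98 points at 2.5% and 1.41 at 1.25%, so the shift is 21% or 29% of it.

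**Between-arm difference.** The SAP formula is difference ± 1.96 × √(SE² + SE²), here with equal arms before the loss.

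- 6 events per arm: from 0 ± 2.79 to −0.41 ± 1.96 × √(0.926² + 1.008²), that is −3.09 to 2.27.
- 3 events per arm: from 0 ± 1.99 to −0.41 ± 1.96 × √(0.589² + 0.717²), that is −2.23 to 1.41.

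These signs apply if the SCC is lost from the ingenol mebutate arm. If it is lost from the imiquimod arm, the signs reverse.

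**How often.** The documents give neither the share of subjects biopsied nor the share of results missing. Assume 5-20% and 2-10%.

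- Subjects affected per arm: 240 × 5% × 2% = 0.24, up to 240 × 20% × 10% = 4.8.
- With a later SCC at the planning risk: 0.24 × 1.0% = 0.0024, up to 4.8 × 2.5% = 0.12.
- Expected shift: these counts × 100/240 = 0.001 to 0.05 points.
- If suspicion raises the risk fivefold (also assumed): 0.012 to 0.6 SCCs, or 0.005 to 0.25 points.

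This applies the full three-year risk after the biopsy, which overstates the loss for later biopsies.

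**Unread biopsy with no SCC.** One such subject, censored early in an arm with 6 SCCs, gives 6/239 = 2.51%; five give 6/235 = 2.55%.

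**Which reading the text favours.**

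- The endpoint in SAP 7.3.2 covers the whole trial period and is timed to the first SCC.
- The SCC row of Table 1 is unconditional.
- SAP section 5 says that the SAP elaborates on the protocol, and the list of changes in SAP 7.5.6 includes no rule that discards confirmed SCCs.
- The missing no-SCC condition is weak evidence for the other reading, because the death row has none either.

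**The case for a change.** The strongest case for a change is that a Kaplan-Meier dataset holds one time and one status per subject, so two programmers could derive different primary results from the same data. The sponsor wrote the no-SCC condition in neighbouring rows, and one precedence sentence, a Missing row in Shell 4 and a small sensitivity table would cost little. It stands that no precedence is stated, that no planned analysis tests the rule and that censoring on suspicion may be informative.

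The proposed remedies gain little:

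- A precedence sentence would record what the endpoint already implies. It would also keep the weakness of that handling: subjects with an unread biopsy contribute their later SCCs but lose their SCC-free follow-up, so censoring depends on the future. The effect is the 2.51% or 2.55% shown above.
- Ignoring the missing result and continuing follow-up presumes that the unread biopsy was negative.
- Counting every missing result as SCC overstates incidence when the lesion was something else: 7/240 = 2.92% for one and 8/240 = 3.33% for two. Actinic keratosis and no malignant findings are both listed outcomes in Shell 4.
- An SCC that went unread and was never confirmed later is the case that censoring cannot recover. Only that worst-case count covers it, and the planned primary estimate would stay as it is.

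Nor would a dropped SCC be hidden. Every SCC inside the treatment area is recorded and reported as an SAE before and after Week 20 (protocol 10.7.5.1, Tables 2 and 3). SAP Table 2-46 counts skin malignancies inside the area, Shell 4 counts invasive SCC by arm, and Shell 5 sets subject and event counts beside the cumulative incidence. A mismatch with the Kaplan-Meier estimate could be seen there.

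**Conclusion.** The omission is real, but it is a gap that analysts fill sensibly, and no change to the plan is needed. Losing one SCC would cost about 0.41 points in the affected arm. That requires an unread biopsy, a later confirmed SCC in the same subject, and the reading that fits the endpoint less well. On the assumed rates the expected loss is 0.001 to 0.05 points per arm, or up to 0.25 points with a fivefold risk, against half-widths of 1.41 to 1.98 points. One lost event would not alter how the difference is read, and no formal between-arm test is planned.

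The number of missing results is unknown. It is probably small, because the central laboratory has at most two weeks to report (protocol 10.7.4.1). How individual cases were handled may already be settled in the analysis set definition document: the SAP is dated August 2019, after the planned completion in Q2 2018. A large number of missing results concentrated in one arm would weaken this conclusion; nothing in the documents points to one.

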## **9 TRIAL OBJECTIVES**

### **9.1 PRIMARY OBJECTIVE**

To compare the cumulative incidence of SCC after treatment with ingenol mebutate gel and imiquimod cream.

The primary response criterion is diagnosis of SCC (defined as invasive SCC i.e. excludes SCC in situ) in the treatment field across the 3-year trial period.

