### 10.3 NUMBER OF SUBJECTS/SAMPLE SIZE

A total of 480 subjects will be enrolled in the trial and randomised 1:1 to the two treatment groups. With 240 patients in each treatment group an adequate precision of the 3-year incidence rate can be obtained. Assuming a 3-year rate of 1.0%, the upper 95% confidence limit

---

will on average be 2.26%, and assuming a 2.5% rate, the upper 95% confidence limit will on average be 4.48%.

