## 10.10.6 Safety Analysis

### 10.10.6.1 Analysis of Primary and Secondary Safety Endpoints

The primary endpoint and secondary safety endpoint are listed in sections [10.9.1](#) and [10.9.2](#) respectively. Both endpoints will follow the same method of analysis.

The 3-year cumulative incidence will be calculated for each treatment group using methods of survival analysis for estimation of cumulative incidence in the presence of censored time-to-event data. Annual incidence rates will also be presented for each group. The cumulative incidence rates will be presented for the event of SCC as primary endpoint and for SCC and other neoplasia as secondary. No formal statistical test comparing the two arms will be performed. For descriptive purposes, as an additional analysis, the difference in cumulative incidence rates between the two arms will be estimated and presented together with its 95% confidence interval.

A landmark analysis, conditional on patients' responses at Week 20, will additionally be performed in order to exclude SCC and other neoplasia reported within the first 20 weeks which are not assumed to be associated with the study treatment. Patients who experience a neoplasia before the 20-week landmark time point are excluded from the time-to-event analysis, which is otherwise conducted as above.

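### Death is censored and incidence is 1 minus Kaplan-Meier, so the reported 3-year SCC figure is the risk if nobody died and slightly overstates the actual probability

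*SAP*

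**What the plan says.** The primary objective (Protocol 9.1) is "To compare the cumulative incidence of SCC after treatment with ingenol mebutate gel and imiquimod cream". The endpoint in SAP 7.3.2 is "diagnosis of SCC (defined as invasive SCC, i.e. excluding SCC in situ) in the treatment field across the 3-year trial period".

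For the method, Protocol 10.10.6.1 asks for "methods of survival analysis for estimation of cumulative incidence in the presence of censored time-to-event data". It names no estimator and does not mention competing risks. SAP 7.3.1 supplies the censoring scheme and notes that the protocol does not detail one. In its Table 1:

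- "Death from any cause" is censored at the date of death.
- Trial discontinuation is censored at the last visit with an assessment and no SCC.

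SAP 7.3.2 gives the estimator: "Cumulative incidence will be presented by 1 minus the survival curves estimated using the Kaplan-Meier method". The arm contrast is the "difference between the Kaplan-Meier estimates of each treatment group", with an interval built from the Kaplan-Meier standard errors. SAP 7.3.3 analyses SCC and other neoplasia in the same way.

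Neither document plans a competing-risk estimate or a sensitivity analysis for death, and neither states an expected death rate. The changes to the protocol listed in SAP 7.5.6 do not touch the point.

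**The concern.** Death ends the possibility of an SCC diagnosis. Censoring it treats subjects who died as if they went on to face the same SCC risk as those still followed. The result estimates what would be seen if nobody died, provided that death is unrelated to SCC risk. That is a legitimate quantity, but it is not the proportion of treated subjects who receive an SCC diagnosis within 3 years, and the SAP does not say which of the two its cumulative incidence means.

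Death is a realistic event here. Follow-up lasts 3 years, the inclusion criteria set no upper age limit, and SAP 7.1.2 plans a summary for subjects aged 85 and over. The estimated incidence is itself the primary result, because no formal comparison is planned, and the trial is a post-approval commitment to the EMA (Protocol 8.2.1). The number should therefore match its label.

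**Working it through.** **Step 1. Reproduce the planning figures.** Protocol 10.3 says "With 240 patients in each treatment group an adequate precision of the 3-year incidence rate can be obtained", with average upper 95% limits of 2.26% at a 1.0% rate and 4.48% at a 2.5% rate. The Wald limit is p + 1.96 × √(p(1 − p)/240).

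- p = 1.0%: half-width 1.259 points, upper limit 2.259% (stated 2.26%).
- p = 2.5%: half-width 1.975 points, upper limit 4.475% (stated 4.48%).

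Both reproduce. These half-widths are the yardstick below.

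**Step 2. Actual cumulative incidence when 1 minus Kaplan-Meier equals F.** Assume constant, independent hazards and 3-year mortality d. The documents give no d, so a range is used. Over the 3 years:

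- SCC: hs = −ln(1 − F)
- death: hd = −ln(1 − d)
- actual cumulative incidence: CIF = hs/(hs + hd) × (1 − exp(−(hs + hd)))

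Example with F = 2.5% and d = 10%: hs = 0.02532, hd = 0.10536, sum 0.13068, exp(−0.13068) = 0.8775. So CIF = (0.02532/0.13068) × 0.1225 = 2.37%.

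| F | Assumed d | CIF | Overstatement (points) | Relative to CIF | Share of half-width |
|---|---|---|---|---|---|
| 1.0% | 5% | 0.975% | 0.03 | 2.6% | 2% |
| 1.0% | 10% | 0.949% | 0.05 | 5.4% | 4% |
| 1.0% | 15% | 0.923% | 0.08 | 8.3% | 6% |
| 2.5% | 5% | 2.437% | 0.06 | 2.6% | 3% |
| 2.5% | 10% | 2.373% | 0.13 | 5.3% | 6% |
| 2.5% | 15% | 2.308% | 0.19 | 8.3% | 10% |

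The largest entry, 0.19 points, is 0.46 of one subject in an arm of 240.

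**Step 3. Check by simulation.** At each of the two rates, 4,000 arms of 240 subjects were simulated with 9% three-year mortality. Mean 1 minus Kaplan-Meier against mean Aalen-Johansen was 1.020% against 0.974%, and 2.495% against 2.381%. Kaplan-Meier gave the higher or equal value in every simulated arm.

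**Step 4. Arm difference.** Allocation is "randomised 1:1 to the two treatment groups", so the half-width of the difference is 1.96 × √(2p(1 − p)/240), which is 1.78 points at 1.0% and 2.79 at 2.5%. With equal mortality and equal net risk the overstatement cancels. If net risk is equal but mortality is 5% in one arm and 15% in the other, the difference in actual cumulative incidence is 0.975 − 0.923 = 0.05 points, or 2.437 − 2.308 = 0.13 points. Kaplan-Meier would show no difference.

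**Step 5. Secondary endpoint.** The documents state no planning rate. At assumed rates of 5% and 10% with 9% mortality, the overstatement is 0.23 and 0.45 points, against half-widths of 2.76 and 3.80. The relative size is again just under 5%.

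**Step 6. Censoring dates in Table 1.** Subjects who die stay at risk until the date of death, although nobody has examined the field since the last visit. Discontinued subjects leave at the last assessment. The extra SCC-free time lowers the estimate. Assume 9% mortality, an average gap of 3 months and a 2.5% rate. The added time is 0.09 × 0.25 = 0.0225 years per subject, out of roughly 3 − 0.09 × 1.5 = 2.865 years, or 0.8%. That is about 0.02 points, against an overstatement of 0.11 points in the same scenario.

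**The case against.** The best case for the plan is that it is a choice of estimand. The protocol asks for survival methods with censored data, and 1 minus Kaplan-Meier is a natural reading of that. If the question is whether a product carries added tumour risk, net risk is a fair answer. Under differential mortality it is the actual cumulative incidence that moves, making the arm with more deaths look safer. This stands. It is why Aalen-Johansen should be added beside Kaplan-Meier, and why the documents do not support the reading that the plan departs from the protocol or that only one estimator is correct.

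The effect is also immaterial beside the sampling error, conservative for each arm's absolute risk, and linked to no test or margin. That stands too. In addition, Shell 5 shows the crude proportion with SCC next to the Kaplan-Meier figure. Over the same period the crude proportion cannot exceed Aalen-Johansen, so the two printed figures bracket it. This helps a careful reader but does not tell anyone what the headline figure means.

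Two further inferences go too far. One is that a competing-risk analysis needs no new data. Table 1 and Listing 7-1 presuppose death dates. However, after Week 20, for events outside the treatment area other than BCC and SCC, only treatment-related SAEs are recorded (Protocol 10.7.5.1, Table 3, and 10.7.6.1), so the completeness of later deaths is not assured. The other is that it would cure the mixed censoring dates. It would not: subjects who die would still be at risk until death, and discontinuations would still end at the last assessment.

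**Conclusion.** The point holds as a minor one. The plan's rule yields the SCC risk if nobody died, under a label that most readers will take as the actual probability of diagnosis. Relative to Aalen-Johansen on the same data, the direction is certain: never lower, and higher whenever a death precedes a later SCC. With assumed 3-year mortality of 5% to 15% and constant independent hazards, the excess is 0.03 to 0.08 points at a 1.0% rate and 0.06 to 0.19 points at 2.5%. That is 2% to 10% of the per-arm half-width. It largely cancels in the arm difference if mortality is similar.

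A reader might infer that the primary result or the sample size is unsound. Neither follows: the planning figures reproduce and are unaffected, and no conclusion in the plan turns on shifts of this size. The differing censoring dates for deaths and discontinuations are a separate, smaller inconsistency that works the other way and does not reverse the overstatement in the example worked.

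**What to change.** For the primary and secondary safety endpoints:

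1. Add the Aalen-Johansen cumulative incidence at 3 years with its standard error per arm, and the arm difference with an interval from those standard errors. Death is a competing event at the date of death.
2. Report it beside 1 minus Kaplan-Meier. State that Kaplan-Meier gives the net risk and Aalen-Johansen the actual cumulative incidence.
3. Tabulate all deaths by arm. Appendix I has a listing of deaths and tables of adverse events by outcome, but no table of all deaths.
4. Confirm how complete death dates are after Week 20, and state any gap with the result.
5. Note in Table 1 why deaths are censored at the date of death and discontinuations at the last assessment, or align the two.

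The cost is a small addition in the same procedure, a few SAP sentences and some extra table rows. The added figures will differ only slightly from those planned, and they are only as good as the death dates.
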